1.0 Overview

1.1 Title

Comparative Effectiveness of Interventions to Improve Screening among Rural Women: Rural Interventions for Screening Effectiveness (RISE)

1.2 Introduction

A multi-disciplinary research team from The Ohio State University and Indiana University School of Nursing will develop and implement an intervention testing the comparative effectiveness of a tailored interactive computer program delivered via DVD (TIDVD) vs. a TIDVD + telephone-based patient navigation (PN) intervention (TIDVD + PN) vs. Usual Care (UC) to increase guideline-based screening rates for Breast Cancer(BC), Cervical Cancer(CC), and Colorectal Cancer(CRC) among women age 50 to 74 living in 32 rural counties of Ohio (OH) and Indiana (IN).

1.3 Aims and Hypotheses

The specific aims are to:

- Aim 1: compare the effectiveness of a tailored and interactive DVD (TIDVD) vs. TIDVD + telephone-based PN intervention (TIDVD + PN) vs. UC, to increase guideline-based cancer screening rates at 12 months post randomization for BC, CC, and CRC among 1058 women age 50 to 74 living in rural northwest Ohio and northeast Indiana
- **Hypothesis 1:** Women in the TIDVD+TPN group will have higher rates of within guideline adherence to all screening tests via MRR at 12 months compared to those who receive the TIDVD alone or UC.
- **Aim 2:** compare the cost effectiveness of the TIDVD and the TIDVD + PN intervention vs. UC, for adherence to each screening outcome or combination of screening tests.
- **Hypothesis 2:** The TIDVD + TPN intervention will be more cost-effective than the TIDVD intervention or UC for adherence to each or combination of screening tests.

We will also identify associations between theoretical variables (community, social, and individual) and screening outcomes, including interactions with the interventions. If found to be cost effective, either or both interventions have the potential to be immediately disseminated to increase BC, CC, and CRC screening rates and ultimately reduce cancer disparities for underserved rural women. This project will use an overall theoretical framework to understand health disparities that includes individual, social and community level variables, and a conceptual model for the intervention which uses a multiple behavior theoretical approach, all of which have demonstrated efficacy in improving adherence to single screening test behaviors, as well as other preventive health behaviors.

2.0 BACKGROUND AND RATIONALE

2.1 Magnitude of the Problem

The cancer burden among rural and underserved populations is significant. Residents living in rural areas in the U.S. experience higher cancer incidence and mortality rates, as well as lower screening rates.¹⁻⁵ The breast cancer mortality rates in the 32 targeted Ohio and Indiana counties are 9.7% and 5.8% greater, respectively, than that for the U.S., while the cervical cancer mortality rate is 12.5% greater, and the CRC mortality rates are 10.4% and 6.1% greater, respectively, than that for the U.S. This results in 106 excess deaths in these counties per year. Reasons for cancer disparities among rural populations are due to many social determinants of health including lower socioeconomic status (SES), lower educational levels, lifestyle factors, genetics, limited access to healthcare, lack of health insurance, or a combination of these factors.³⁻⁶ Screening adherence rates for BC, CC, and CRC cancers, for which there are validated screening tests available, are lower for those with less education, a proxy for SES.^{7,8} The rural counties targeted for this project (Figure 1), include mainly White, poorer, and less educated populations with limited access to health care. Thus, it is essential to intervene in these rural counties to reduce cancer disparities. Many rural women do not complete screening at recommended intervals.⁵ In a recently completed observational study among rural women in Ohio, medical record validated completion of screening within recommended guidelines was: 32% for mammography, 36% for Pap test, and 30% for a CRC test.⁹ Only 8.6% had completed all three tests within guidelines.⁹This suggests the need for cost effective interventions to provide rural women with the latest information about screening recommendations and needed tests.^{10,11}

2.2 Justification for the Study

The significance of this study is enhanced by the potential to develop a stronger more efficacious intervention through the combination of two previously tested interventions (tailored interactive programs and patient navigators). This research will test the hypothesis that the addition of a Patient Navigator (PN) to the tailored program will be more effective than a tailored approach alone or UC. This study will determine the cost-effectiveness of interventions that vary in complexity, time, and cost. We will determine if adding a telephone-based PN will be worth the additional costs by comparing the TIDVD intervention with and without PN vs. UC.

2.3 Intended/Potential Use for Study Findings

If either or both interventions are shown to be cost-effective compared to UC to improve screening rates, they can be quickly/easily disseminated to rural areas where access to health care is suboptimal, and cancer mortality rates for CC, BC, and CRC are higher than non-rural areas.

3.0 METHODS

3.1 Research Design

3.1.1 Participants

Our study will target women aged 50 to 74 who reside in 32 rural counties in northwest OH and northeast IN (Figure 1). In these counties (2010), there were 173,812 women in the appropriate age category, 96% who are White (non-Hispanic). We will enroll 1058 women 50-74 years in the designated counties, stratified by Rural Urban Commuting Area (RUCA) code. U.S. Preventive Services Task Force cancer screening guidelines will be used for all screening tests to determine eligibility (Table 1).

Figure 1. Map of Intervention Counties

[figure not shown]

Table 1. United States Preventive Services Task Force Screening Guidelines

Site	Guideline
BC	Women ages 50-74: mammogram every 2 yrs.
CC	Women ages 50-65: Pap test every 3 yrs. or Pap test and HPV co-testing every 5 yrs. Discontinue after age 65 for women with 3 consecutive negative cytology results or 2 consecutive negative HPV results in last 10 yrs.
CRC	Women ages 50-75: stool test (FOBT/FIT) annually or colonoscopy every 10 yrs. For those at increased risk; colonoscopy is recommended.

3.1.2 Eligibility criteria. To be eligible, women must:

- 1) be aged 50-74 years (inclusive);
- 2) be non-adherent to one or more recommended screenings for BC, CC, or CRC by MRR;
- 3) reside in one of 32 rural counties in IN or OH;
- 4) provide informed consent;
- 5) able to speak/read English; and
- 6) have access to a DVD player or computer that can play DVDs.

3.1.3 Exclusion Criteria. Women will be excluded if they:

1) have a personal or family history of any hereditary/genetic cancer syndrome such as BRCA1 and BRCA2 polymorphisms, hereditary nonpolyposis colon cancer, or familial adenomatous polyposis;

2) have a personal history of inflammatory bowel disease (Crohn's disease or colitis), colon polyps, or a history of cancer except non-melanoma skin cancer;

[figure not shown]
3) have more than one first degree relative with a history of colorectal cancer or one first degree relative who was diagnosed with colorectal cancer before the age of 60;

4) plan to move outside of the country within the next year;

5) reside in a nursing home or other institution; or

6) are pregnant or intend to become pregnant during the study period.

Figure 2: Study Schema

3.2 Recruitment Process:

3.2.1 Sample Selection

Eligible female residents of each of the 32 study counties will be randomly selected from a customized list provided by Marketing Systems Group (white pages, commercial and United States Postal Service (USPS) lists) that includes female county residents age 50-74, inclusive (N=173,812). In order to ensure a sufficient number of truly rural women are enrolled, the sample selection will be stratified by Rural-Urban Commuting Area (RUCA) code which is assigned at the census tract level. An equal number of women will be sampled from tracts with RUCA codes of 4-6 and 7-10. Codes 4 through 6 represent micropolitan areas in and around towns with 10,000-50,000 residents where some residents may commute to a larger urban core. Codes 7 through 10 indicate small towns (population 2,500-9,999) and rural areas with little commuting to larger urban clusters. [name] will provide selected names monthly to the OSU Behavioral Measurement Shared Resource (BMSR). We estimate that 55% of the women will be eligible and 70% of eligible women will participate; thus to achieve our sample size of 1058, we will need to mail approximately 2,750 letters.

In addition to mailing and calling, promotional materials encouraging women in these regions to volunteer to participate in the study will be placed within the target communities. Promotional materials (flyers/brochures/postcards) may be displayed within public spaces where women in the age group may frequent, such as libraries, senior centers, health departments, etc. to promote the study and increase credibility. OSU CCTS Recruitment and Retention Services and potentially IU CTSI Research Recruitment Program will be employed to promote the study. We are requesting the use of Research Match (ResearchMatch.org) and Study Search (studysearch.osumc.edu) for participant recruitment on this protocol. Through these promotional materials and advertisements, potentially eligible women will be encouraged to call study staff via a toll-free number to determine eligibility and schedule a call with an interviewer to complete the consent process and baseline survey.

Targeted Facebook ads will be posted to 50-year-old and older women's Facebook pages who live in counties of interest. These ads will be promoted by the OSUMC Communications and Marketing team through The Ohio State University and Wexner Medical Center Facebook pages.

3.2.1.a Phase 2 Sample Selection (beginning January 2018)

The recruitment area will be expanded to additional rural counties in both Indiana and Ohio (see map – Figure 3) in order to improve enrollment rates. Promotional materials will be sent to locations in these communities and Facebook ads will target these additional counties. Mail/call lists of female residents may be purchased for these additional counties as well. Craigslist advertisements will be developed and placed on community pages for the geographic areas from which we are recruiting.

[figure not shown]

Figure 3. Map of Recruitment Area

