3.2.4 Eligibility Verification

After completion of the baseline telephone survey, participants will be mailed a medical record release form with a stamped, pre-addressed envelope to mail the medical record release form back to the OSU study office. Those who do not return the release form within two weeks will be re-contacted by the interviewer. Study staff will review and verify screening tests received by MRR and if the woman is still eligible, she will be enrolled and randomized to one of 3 study arms. The trained interviewers will be familiar with screening, determining eligibility, administering telephone surveys, and have a keen understanding of rural culture.

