3.3 Randomization

Once eligibility is confirmed via medical record review, participants will be randomly assigned to one of 3 study arms -1)TIDVD alone, 2)TIDVD + PN, or 3)UC. A centralized web-based system at OSU will be used to randomize participants to one of the 3 study arms. Randomization will be stratified by age (50-64 vs. 65-74) and by seven screening categories representing which screening test(s) each woman needs (BC, CC, CRC, BC+CC, BC+CRC, BC+CC+CRC, or CC+CRC).

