3.4.2 Community-Level Variables

Effect of community (neighborhood) factors, using geographic information system (GIS), on outcomes of

receipt of needed screening tests will be evaluated. Participant addresses will be geocoded and accessibility to health care will be determined by measuring the number of facilities within a given distance of each geocoded address. Geocoded addresses will be spatially joined to a U.S. Census Topologically Integrated Geographic Encoding and Referencing (TIGER) zipcode shapefile containing demographic data. An area deprivation index score will be created using the health care accessibility variable and 21 U.S. Census data variables, including social and economic conditions (e.g. education, employment/occupation, housing conditions, income/ poverty, racial composition, residential stability).¹²⁻¹⁵ **3.5 Incentives**

A total of \$25 in incentives will be distributed to participants as a sign of gratitude for taking the time to complete and return the surveys. Amounts and timing are detailed in Table 3.

Table 3. Gift Card Distribution

Time	Action	Amount
Pre-enrollment	Complete phone survey and send medical record release	\$5
Baseline	Complete and return paper survey	\$10
Month 12	Complete and return paper survey	\$10

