3.8 Medical Record Review (MRR)

Participants will be asked to sign and return a MRR form to the study office after the baseline interview. The signed release will remain valid for the duration of the study. Dates and results of completed BC, CC, and CRC screening tests and confirmation of participant date of birth (DOB) will be requested from health care providers named by participants during the baseline and 12-month interviews. We are confirming DOB to ensure that records are obtained for the correct woman. The MRR form signed by the participant along with a request from our research office will be presented to the medical facility (secure fax, phone, secure email, or in-person) where the cancer screening tests were ordered or performed. This request will inform the clinic/facility staff about the study and request information from the medical record about the participant's cancer screening history to be sent to a secure fax or mailed to the study office at OSU. Women who report never being screened and/or cannot produce provider names or locations will be asked to complete MRR forms in order to contact locations that they may visit for screenings during the study period. Non-responders will be contacted again, if necessary, to obtain this information. We anticipate that at least 85% of the participants will return a signed MRR form, and 95% of clinics will respond to our request for information (based on our prior studies).¹⁶

[figure not shown]

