5.0 Data Handling and Analyses

5.1 Statistical Analysis

5.1.1 Sample Size

Estimates of effect size (Table 5) for the intervention at 12 months is based on our experience in projects promoting screening among underserved populations. We estimate 10% attrition at 12 months, when our primary outcome will be assessed. Attrition of 10% is conservative because we will have medical record data on most of the persons who drop out which will reduce the effect of drop out on the primary outcomes. We based power calculations on 2-sided tests when comparing the two intervention arms (TIDVD vs. TIDVD+PN) because we could not be certain which group would perform better. Because of the overwhelming evidence in the literature^{35,36} that the UC arm does not have better screening rates than tailored DVD or PN interventions, we based the power calculations on 1-sided tests for comparisons to the control group (TIDVD vs. UC; TIDVD+PN vs. UC). The planned statistical analyses are consistent with these power calculations. Specifically, we will use two sided tests for TIDVD vs. TIDVD+PN, and the 1-sided tests for comparing interventions to the UC arm, using the 1-sided p-value from the Z statistic in contingency table analysis and from the likelihood ratio test in logistic regression analysis. To achieve 80% power for the contingency table analyses, and the likelihood ratio tests of logistic regression for the primary outcome of adherence to all needed screening tests at 12 months by MRR, a sample size of 356 per each intervention group and 180 in the UC group will be needed, which will require 396 per intervention group and 200 in the UC group at baseline to account for attrition. For 80% power for the secondary outcome of adherence to any needed (BC or CC or CRC) test, regardless of the number of screening tests needed, a sample size of 376 per each intervention group and 200 in the UC group will be required at 12 months. We will require 418 per intervention group and 222 in the UC group at baseline to account for attrition and to achieve at least 80% power for both outcomes. The total sample size is 1058 participants enrolled with 418 randomized to each intervention arm and 222 randomized to the UC arm.

Table 5.	Samp	le Size'
----------	------	----------

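### Does the 2,750-letter mailing estimate leave out women who never return the medical-record release?

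*Combined protocol and SAP*

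**What the plan says.** Section 3.2.1 gives two planning rates, "We estimate that 55% of the women will be eligible and 70% of eligible women will participate", and from them the mailing volume: "thus to achieve our sample size of 1058, we will need to mail approximately 2,750 letters".

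The steps between letter and randomisation are set out elsewhere:

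- Section 3.2.3: eligibility screener, verbal consent, then the baseline telephone survey.
- Section 3.2.4: the release form is mailed after that survey. Staff then check the records, and "if the woman is still eligible, she will be enrolled and randomized to one of 3 study arms".
- Section 3.3: "Once eligibility is confirmed via medical record review, participants will be randomly assigned to one of 3 study arms".
- Section 3.5, Table 3: the first gift card, which falls before enrolment, is for this action: "Complete phone survey and send medical record release".
- Section 3.8: "We anticipate that at least 85% of the participants will return a signed MRR form". A single form serves throughout: "The signed release will remain valid for the duration of the study".

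Section 5.1.1 fixes the target: "The total sample size is 1058 participants enrolled with 418 randomized to each intervention arm and 222 randomized to the UC arm".

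**The concern.** The letter count is used up by eligibility and participation. Returning the release is a further step before randomisation, and the protocol gives it an expected rate below 100%. Sections 3.2.4 and 3.8 already call women participants when the form is sent to them. Read that way, the 70% who participate are counted before form return, and a third factor is missing.

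At stake would be the recruitment workload: letters, follow-up calls and baseline telephone surveys. If mailing stopped at 2,750 letters and nothing else brought women in, enrolment could end below 1058.

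**Working it through.** **Inputs.** Target 1058 (section 5.1.1); 0.55 eligible and 0.70 of those participating (section 3.2.1); form return of at least 0.85 (section 3.8).

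**The plan's own figure.** Letters = N / (eligible x participating) = 1058 / (0.55 x 0.70) = 1058 / 0.385 = 2,748, which rounds to the stated 2,750. Forwards, 2,750 x 0.385 = 1,058.75. The two rates account for the whole figure, so it is arithmetically correct on its stated inputs.

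**If the two rates are counted before form return.** Divide further by the return fraction r:

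| r | Letters for 1058, = 1058 / (0.385 r) | Randomised from 2,750 letters, = 1,058.75 r | Consented women needed, = 1058 / r |
|---|---|---|---|
| 0.85 (stated floor) | 3,233 | 900 | 1,245 |
| 0.90 | 3,053 | 953 | 1,176 |
| 0.95 | 2,893 | 1,006 | 1,114 |

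At the floor this is 3,233 - 2,750 = 483 more letters and 1,245 - 1,058 = 187 more telephone surveys. With only 2,750 letters, enrolment would be 1058 - 900 = 158 women (15%) short. The 0.90 and 0.95 rows are assumptions that show the range above the floor.

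Section 3.8 also expects 95% of clinics to respond. Treating that as a loss per woman that bars randomisation is an extra assumption. It gives 1058 / (0.385 x 0.85 x 0.95) = 3,403 letters.

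**If the two rates already include form return.** 2,750 stands. Participation by telephone alone would then have to be 0.70 / 0.85 = 82% of eligible women at the 85% floor.

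**Which reading the text supports.** Three places bear on it.

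- Section 3.1.2 makes non-adherence by record review an eligibility criterion, so the 55% can be read as a rate after review.
- Section 3.2.1 applies the 70% directly to the 1058. Section 5.1.1 describes those women as enrolled, and section 3.2.4 puts enrolment after the review. On that chain the 70% already includes form return.
- Section 5.1.2 plans imputation for women lost to follow-up who signed no release, and uses self-report where records are missing. This leaves some doubt whether the 85% is strictly a loss before randomisation.

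The wording of sections 3.2.4 and 3.8 points the other way. Section 3.2.1 does not define participation, so the question stays open.

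**Would power suffer?** Only if enrolment stopped short. As an illustration, take 900 randomised in the planned ratio, 10% attrition, and an assumed alpha of 0.05 (two-sided between the interventions, one-sided for TIDVD against usual care). This leaves about 320 per intervention arm and 170 in usual care. Under the normal approximation, power for the secondary outcome, which sets the total sample size, falls from 80% to 73-74%. For the primary outcome these two comparisons stay at 83% or more (89% and 94% at full enrolment by the same formula, which exceeds the 82% and 83% printed in Table 5). Nothing in the plan calls for stopping at 900.

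**The case for a change.** The strongest case for a change is that the reading counted before form return is the more natural one. The protocol calls women participants before the form comes back, and no telephone participation rate of 82% appears anywhere. Other recruitment routes may reduce the number of letters, but women who arrive that way must also consent, complete the survey and return the form. At 85% return, about 1,245 consented women are needed whatever their source. The remedy would be one sentence or one revised number.

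Much of this stands. The sums are right, the order of steps is clear, and the two rates are undefined. What does not stand is the flat claim that the estimate is too low. That depends on a reading the text leaves open, and the 85% is a floor, with section 3.2.4 providing for re-contact of women who do not return the form. At 95% return the difference is 143 letters, about 5% of a number given as approximate. Nor is form return the only unlisted loss. Section 3.2.2 expects some women to be unreachable after ten calls, yet no contact rate is stated. Either the two rates are meant to cover every loss, or the estimate is rough in several respects.

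**Conclusion.** No change to the plan is needed. The letter count is correct on its stated inputs. It would be low by up to about 480 letters (about 18%) at the 85% floor if the two rates are counted before form return, and not low at all if they include it. The documents do not settle which. The 3,403 figure rests on the further assumption about clinic response.

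The figure steers logistics only. The sampling list covers 173,812 women, with names released monthly. Section 3.2.1 adds community materials, online registries and Facebook advertising, and section 3.2.1.a widens the recruitment area and allows further list purchase. A low yield would show up during recruitment and be met by more mailing, at the cost of letters, calls and telephone surveys. The enrolment target, the outcomes and the tests are unaffected, and power is preserved as long as recruitment continues to 1058. This is a gap in a planning estimate that the study team can fill as it goes; defining the two rates would tidy the text but would not alter the trial or its conclusions.
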